17.7.2. Modified ITT (mITT) Population

The modified Intent-to-Treat (mITT) population will be defined as all subjects who are enrolled into the study, received any study drug, and did not fail Exclusion Criterion #2. Subjects in this population will be analyzed according to the cohort to which they were allocated. All efficacy analyses will be performed on the mITT population.

17.7.3. Per Protocol Population

Subjects without violations or major deviations will be included in the Per Protocol Population. All efficacy analyses will be repeated on this population.

17.7.4. Face Subpopulation

Subjects whose Treatment Fields are located on their face (i.e., cheeks or forehead) will constitute the ITT-Face, mITT-Face, and PP-Face populations.

17.7.5. Pharmacokinetic Population

Not applicable.

17.8. Definitions of the Terms Violation and Deviation

Violation – Any enrolled subject who does not meet the study enrollment criteria (see Inclusion and Exclusion Criteria in Section 9) will be considered a violation.

Deviation – Any activity that diverges from the procedures defined by this clinical protocol will be considered a deviation.

A **major deviation** is one that will definitely, probably, or possibly significantly impact the subject safety or the quality of the trial data. An example of a major deviation is a subject who missed dosing >7 consecutive days of study drug.

A **minor deviation** is one that does not, or is unlikely to, significantly impact subject safety or the quality of the trial data.

All violations and deviations must be recorded in the study site's electronic system and signed by the Investigator (or designee).

A Violation and Deviation Review Meeting that includes members of the study team from the Sponsor and the Statistical Management CRO will determine which subjects meet the above definitions. Details of this meeting will be included in the Statistical Analysis Plan. It is the Sponsor's responsibility to determine whether the event will be considered a violation, major deviation, or minor deviation.

17.9. Subject Compliance

Subjects will record administered and missed doses in their Dosing Diaries. Study drug tubes will also be weighed at each site visit.

17.10. Demographic and Baseline Characteristics

The comparability of the cohorts will be summarized by the evaluation of the demographic information, including age, gender, and country.

18. STUDY MANAGEMENT AND DATA COLLECTION

18.1. Data Collection Methods

Trained investigational site staff will enter the data required by the protocol into the eCRFs from source documents. All information on the eCRFs must be traceable to these source documents. Instances of missing or uninterpretable data will be discussed with the study site for resolution. The study site is responsible for providing missing data and resolutions to the data queries and for correcting the eCRFs as appropriate. eCRFs must be reviewed, signed, and dated by the Investigator. All original laboratory and ECG reports will be kept with the subject source documentation and a copy will be transmitted to the Sponsor (or designee), if required.

ECGs should be transmitted to the central laboratory the same day the data are obtained, if possible.

18.2. Monitoring

Vidac Pharma (or their designee) will conduct site visits to the investigation facilities for the purpose of monitoring all aspects of the study.

18.3. Data Retention

All relevant correspondence (e.g. with the Sponsor, CRO, IRB, etc.) relating to this clinical study conduct should be maintained in the appropriate file at the site.

The Investigator must retain all records, including the source documents, ICFs, laboratory reports including ECGs, and all other study-related documentation for a period of at least 2 years following the date the last marketing application is approved for the study drug for the indication for which it is being investigated, or 2 years after the date that the FDA has been notified that all clinical investigation of the drug has been discontinued, whichever is greater, unless notified otherwise in writing by the Sponsor. These documents should, however, be retained for a longer period if required by the applicable regulations or if requested by the Sponsor. The Investigator must contact the Sponsor and gain written approval prior to destroying any records. No study documents will be destroyed or moved to a new location without prior written approval of the Sponsor. If the Investigator relocates, retires, or withdraws from a clinical study for any reason, all records required for the study should be transferred to an agreed-upon designee, e.g. another Investigator.

19. CLINICAL STUDY ADMINISTRATION, ETHICS, AND CONDUCT

19.1. Good Clinical Practice

GCP is an important ethical and scientific quality standard for designing, conducting, recording and reporting studies that involve the participation of human subjects. Compliance with this standard provides public assurance that the rights, safety and well-being of study subjects are protected.

19.2. Confidentiality

19.2.1. Study Confidentiality

All information regarding the nature of the investigation provided by the Sponsor or its designee to the Investigator and his / her staff or designees (except for information required by law or regulations to be disclosed to the IRB, the subject, and/or the appropriate regulatory authorities) must be maintained in confidence by the Investigator and his / her staff or designees.

19.2.2. Subject Anonymity

The anonymity of participating subjects must be maintained. Subjects will be identified by their initials and subject number on CRFs and other documents submitted to the Sponsor. Documents not submitted to the Sponsor include those that identify the subject (e.g., the signed ICF), and must be maintained in strict confidence by the Investigator, except as necessary to allow auditing by the IRB, Sponsor or its designee, FDA, and/or equivalent authorities.

19.3. Subject Information and Informed Consent

Before being enrolled in the clinical study, subjects must consent to participate after the nature, scope, and possible consequences of the clinical study have been explained in a form understandable to them.

An informed consent document that includes information about the study will be prepared and given to the subject. This document will contain all the elements required by the ICH E6 Guideline for GCP and any additional elements required by local regulations. The document must be in a language understandable to the subject and must specify who informed the subject. Where required by local law, the person who informs the subject must be a physician.

All ICFs must contain the minimum elements as mandated by the FDA and ICH guidelines and will be subject to the Sponsor's (or designee's) approval as well as the IRB's approval.

The Investigator will not undertake any measures or procedures specifically required of a subject for the clinical study until valid consent has been obtained.

If an amendment to the protocol changes the subject participation schedule in scope or activity, or increases the potential risk to the subject, the ICF must be revised, submitted to the IRB for

review and approval or favorable opinion. The revised ICF must be used to obtain consent from a subject currently enrolled in the study only if he or she is affected by the amendment. The revised ICF must be used to obtain consent from any new subjects who are enrolled into the study after the date of the approval or favorable opinion of the amendment.

19.4. Study Closure

Completion or premature termination of the study will be reported by the Sponsor to the regulatory agency and by the Sponsor or by the Investigator to the IRB as required by local regulations or by the IRB.

Once the database is locked, and all efforts are made to settle all outstanding queries, site closeout will occur. Study materials (including used and unused study drug) must be returned, disposed of, or retained, as directed by the Sponsor.

19.5. Early Termination of the Clinical Trial

If, in the opinion of an Investigator, the clinical observations in the study suggest that it may be unwise to continue, that Investigator may terminate their site's participation after consultation with the Sponsor. A written statement fully documenting the reasons for such a termination will be provided to the Sponsor.

The Sponsor may terminate the study at any time for any reason.

If it becomes apparent that subject enrollment at a particular site is unsatisfactory with respect to quality or quantity, or that data recording is inaccurate or incomplete on a chronic basis, the Sponsor has the right to terminate participation of that site and remove all study materials from that investigational site. A written statement will be provided to the Investigator, the IRB, and regulatory authorities, if required.

20. INVESTIGATOR'S OBLIGATIONS

20.1. General

The Investigator agrees that the study will be conducted in accordance with the clinical protocol, ICH-GCP guidelines, and the Declaration of Helsinki. The Investigator will conduct all aspects of this study in accordance with all governmental, state and local laws.

20.2. Institutional Review Board

Before initiation of the study at any site, the Investigator must obtain approval of the clinical protocol and ICF from the IRB complying with the provisions specified in FDA CFR, Title 21, Part 56, ICH Guidelines, and all governmental, state and local laws.

A copy of the written IRB approval of the protocol, ICF and any other documentation (such as advertising) as appropriate must be provided to the Sponsor or its designee prior to initiation of the study. The approval letter must identify the IRB name and address, the clinical protocol by title and/or protocol number, and the date approval was granted. Furthermore, the approval letter must contain a statement that the IRB complies with the FDA CFR, Title 21, Part 56, and ICH Guidelines for a study conducted under an IND, or other applicable government regulations for studies not conducted under an IND.

The Investigator is responsible for supplying the IRB with the data required for continued review of this study at intervals not exceeding one year, or at intervals otherwise specified by the IRB. The Investigator shall supply the Sponsor with written documentation of this continued review. When necessary, an extension or renewal of the IRB approval must be obtained and this shall also be forwarded to the Sponsor. A list of the IRB members should be forwarded to the Sponsor in accordance with local regulations.

The IRB and the regulatory authorities will be provided with any amendments for their review and/or approval. A yearly status report on the progress of the study will be submitted by the Investigator to the IRB per their regulations.

20.3. Investigator Protocol Adherence

The Investigator and his/her designees are required to adhere to the protocol.

In general, protocol deviations will not be granted. However, if a minor protocol deviation is necessary in order to eliminate an immediate hazard to a subject or to facilitate a subject's adherence to protocol procedures, such a deviation request may be communicated to the Study Medical Monitor in writing for their consideration. Such a request should include a clear, complete, and compelling written description and justification. A copy of this request and the written response of the Study Medical Monitor must also be placed in the appropriate file at the site.

Emergency deviations from the protocol that eliminate an apparent immediate hazard to a subject and that are deemed crucial for the safety and well-being of a particular subject may be instituted for that subject only. If time allows, the Investigator must consult with the Study

Medical Monitor. If time does not allow, the Investigator may approve the deviation without prior consultation with the Study Medical Monitor. The Investigator will contact the Sponsor as soon as possible in the case of such a deviation. These deviations do not require pre-approval by the IRB; however, the Sponsor and the IRB must be notified in writing as soon as possible after the departure has been made. In addition, the Investigator will document in the subject's CRF the reasons for protocol deviation and the ensuing events.

20.4. Protocol Amendments

Any additions or changes to the clinical protocol will require a protocol amendment. The Amended Clinical Protocol Signature Page will be signed by the protocol signatories. Protocol amendments must undergo IRB approval prior to implementation. Should the ICF require changes, the revised ICF must be approved also according to the same procedure.

20.5. Audits and Inspections

The Investigator will permit study-related monitoring, audits and inspections by the IRB, the Sponsor or its designee, government regulatory bodies, and quality assurance groups of all study-related documents. This includes direct access to source documents, regulatory documents, data collection instruments, study data, etc. The Investigator will ensure that all study-related facilities (e.g., pharmacy, laboratories, etc.) are maintained in accordance with GCP guidelines.

Participation as an Investigator in this study implies acceptance of potential inspection by government regulatory authorities and applicable Sponsor (or designee) quality assurance personnel.

22. APPENDICES

22.1. Local Skin Reaction Score

The Local Skin Reaction Score is an assessment of the skin in the Treatment Field. At each study visit the Investigator (or designee) will assign a severity score to each of the objective findings listed in the table. **Whenever possible, the same investigator should perform all the LSR assessments.**

The Investigator will assess the selected Treatment Field and rate the findings on a 5-point scale (0-4). The composite LSR score will consist of the sum of all the individual LSR scores.

Local Skin Reaction	0 NONE	1 MILD	2 MODERATE	3 SEVERE	4 EXTREME
Erythema	None or Pinkish-red over isolated portions of the Treatment Field	Pinkish-red over most of the Treatment Field	Red	Intense redness (beet red)	Very intense redness that extends >2 cm beyond the Treatment Field
Edema / Swelling	None or Trace edema	Slightly palpable or barely visible edema	Visible and easily palpable edema	Gross edema	Gross edema that extends >2 cm beyond the Treatment Field
Weeping / Exudate / Crust	None	Mild weeping or exudate	Moderate weeping, exudate or crust	Thick exudate or crust over >50% of the Treatment Field	Heavy exudate or crust that extends >2 cm beyond the Treatment Field
Vesicles / Pustules	None	Vesicles with limited coalescing	Vesicles over >50% of the Treatment Field with majority coalescing	Pustulation	Coalesced pustules
Flaking / Scaling	None or Trace flaking/scale	Mild flaking or light scale	Moderate flaking and/or scaling over >50% of Treatment Field	Severe, thick scale	Severe, thick scale that extends >2 cm beyond the Treatment Field
Erosion / Ulceration	None	Scattered shallow erosions	Deep erosions over >50% of the Treatment Field or limited areas of ulcerations	Small eschar or extensive ulcerations	Eschar that covers the entire Treatment Field

The 5-point LSR Score is: **0 = No or Trace Reaction, 1=Mild Reaction, 2=Moderate Reaction, 3=Severe Reaction, and 4=Extreme Reaction.**

In this trial Local Skin Reactions (LSRs) will not be recorded as AEs unless they (a) require treatment with a prescribed medication; (b) extend >2 centimeters beyond the border of the Treatment Field; or (c) require a study drug dose adjustment.

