11.2. Treatment Field Selection

Any 25 cm² contiguous area on the face or scalp of the subject that contains 4-8 AK lesions that meet the requirements stated in AK Lesion Eligibility criteria (Section 11.1.3) may be selected as the study Treatment Field. The Treatment Field will be selected at Screening and confirmed on Day 1 Pre-Dose. If the Treatment Field selected at Screening is no longer eligible at Day 1 Pre-Dose, a new Treatment Field must be selected on Day 1 Pre-Dose.

The Treatment Field must be a single, contiguous 25 cm² area that is easily visible to the subject when looking in the mirror. The Treatment Field should include at least 4 but not more than 8 AK lesions all of which must be Grade 1 or 2 AK lesions. The ideal Treatment Field should optimally be square or rectangular and not irregular, to simplify study drug application by the subject.

The Treatment Field or its outer border must not be:

- a) An area of skin that received any AK or other medical or physical treatment within 4 months of the Day 1 Visit (Exclusion Criterion #14);
- b) Within 2.5 cm (~1 inch) of either labial commissure of the mouth, lip vermilion border, palpebral fissure or a suspected malignancy;
- c) Close to another active dermatologic process that could spread to the Treatment Field and interfere with the proper assessment of the Treatment Field and/or its included AK lesions;
- d) So close to the eyebrows, beard, or other area with hair as to interfere with proper application of the study drug or assessment of the Treatment Field.

NOTE: Ideally other AKs should NOT be adjacent to the border of the Treatment Field which could confound the AK lesion counting or identification of the Treatment Field at subsequent study visits.

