13.6.4. Study Drug Administration at Home

The study drug will be applied to the Treatment Field by the subject or their dosing partner. Subjects in Cohort 1 will apply approximately 200 mg of 10%VDA-1102 each morning before 10:00 am and each evening at least 3 hours prior to bedtime. Subjects in Cohort 2 will apply approximately 200 mg of 20%VDA-1102 each morning before 10:00 am.

Cohorts 1 and 2: The morning dose should be applied before 10 am. **If a subject knows that they will perspire, shower, vigorously exercise, etc. before 10 am, application of the study drug should be delayed until completion of those activities.**

Cohort 1 only: The evening dose should be applied each day **at least 3 hours** before bedtime.

If the subject would like to shower, wash their face, shampoo their hair, etc., these should be performed prior to study drug application.

At the dosing time, the subject should check the Treatment Field in the mirror to assure it is clean and dry.

The study drug tube will be removed from the container, the tube cover unscrewed, and the study drug ointment expressed as a strip into the rectangle printed on the supplied Dosing Card.

Using a mirror, Treatment Field photograph, and/or the landmarks drawn on the Treatment Field Template, the template will be appropriately positioned on the subject's face or scalp. The subject (or dosing partner) will apply the study drug to the Treatment Field on their skin that corresponds to the 25 cm² area cut out of the template. Subjects (or their dosing partners) will apply the study drug with one finger to the center of the Treatment Field and spread the ointment evenly over the entire field. The Treatment Field will **not** be occluded. The subject will remove the Treatment Field Template from their face. With the same finger, the subject will spread ointment at the periphery of the Treatment Field approximately ¼ inch beyond the Treatment Field perimeter to ensure that the whole Treatment Field was covered with study drug.

After each study drug application, the subject's hands should be very carefully washed with warm water and soap.

The subject will be instructed not to wet or touch the Treatment Field. Subjects should not perform activities that might cause wetting or excessive sweating of the Treatment Field, for approximately 6 hours after dosing.

After each dosing, the Dosing Diary must be completed.

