15.1.2. Local Skin Reactions

In this trial Local Skin Reactions (LSRs) will not be recorded as AEs unless they (a) require treatment with a prescribed medication; (b) extend >2 centimeters beyond the border of the Treatment Field; or (c) require a study drug dose adjustment.

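### Reactions on the ointment-treated skin just outside the Treatment Field, and spread of up to 2 cm, can be missed by both the LSR score and the AE tables

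*Combined protocol and SAP*

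**What the plan says.** Five parts of the protocol bear on this.

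- **Scored area.** Section 22.1: "The Local Skin Reaction Score is an assessment of the skin in the Treatment Field". Section 10.3.7 and the visit lists in 12.6 also place the score in the Treatment Field. In the 22.1 table, four of the six items (erythema, edema, weeping, flaking) mention skin outside the field. They do so only at grade 4 and only beyond 2 cm. The vesicle and erosion items never do.
- **Dosed area.** Section 13.6.4 has the ointment applied to the skin that "corresponds to the 25 cm² area cut out of the template". The template is then removed and the subject is told to "spread ointment at the periphery of the Treatment Field approximately ¼ inch beyond the Treatment Field perimeter".
- **AE rule.** Under section 15.1.2, repeated in 22.1, LSRs are not AEs unless they "require treatment with a prescribed medication", "extend >2 centimeters beyond the border of the Treatment Field", or call for a change in study drug dosing.
- **Physical examination.** Section 10.3.3 includes the skin and requires abnormal findings to be recorded. It counts a skin lesion as clinically significant only if it needs treatment at that examination. Table 1 schedules the examination at Day 1 Pre-Dose and Weeks 4, 8, 12 and 16. LSR scoring is scheduled at those visits and also at Week 13.
- **Field placement.** Under section 11.2 the field or its border must not be "Within 2.5 cm (~1 inch) of either labial commissure of the mouth, lip vermilion border, palpebral fissure or a suspected malignancy".

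**The concern.** The LSR score stops at the field border, and the extent criterion for an AE starts 2 cm beyond it. Skin between the two has no graded record. The inner part of that band receives drug by instruction, so it is not merely neighbouring skin.

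Local skin safety and tolerability is part of the primary objective (section 6), and the results are to inform Phase 3 design and dose selection (section 5.6.4). There is no control arm, so the descriptive LSR and AE tables carry most of the local tolerability evidence for each regimen. Local reactions are plausible. Section 5.6.1 reports reversible skin reactions in 2 of 5 subjects on 10% BID, and section 5.4.2 puts the minipig no-effect level for local findings at 5%, below both study strengths. Where the gap has an effect, it can only make the LSR score and the recorded extent too low.

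**Working it through.** The plan states no figure on this point, so there is none to reproduce. The check has two parts.

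**1. Which record captures which reaction.** Assume that the reaction needs neither a prescribed medication nor a dose adjustment.

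- *Inside the field only:* graded 0-4 on the LSR form. Captured.
- *Inside the field and extending up to 2 cm past the border:* the in-field part is graded. Section 15.1.2 plainly treats this as an LSR and not an AE. The distance is not recorded, so spread of 0.1 cm and of 1.9 cm give the same data. A worse grade outside the border is not recorded either. As an illustration, if erythema is grade 1 in the field and would be grade 3 on the margin, the form shows 1.
- *Confined to the margin:* this depends on what counts as an LSR. If LSRs exist only inside the field, this is not one, and the general AE definition in 15.1.1 applies. If LSRs include nearby skin, 15.1.2 exempts it from AE recording, while the 22.1 form still rates only the field. The protocol does not say which reading holds.
- *Beyond 2 cm:* an AE under 15.1.2(b). Captured.

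**2. How much skin is involved.** Inputs: field area 25 cm² (13.6.4) and margin width d = 0.25 × 2.54 = 0.635 cm (13.6.4). The shape is not fixed, so three convex shapes are assumed. For perimeter P, band area = P × d + π × d², and π × 0.635² = 1.27 cm².

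- Circle, P = 2√(25π) = 17.72 cm: 11.25 + 1.27 = 12.5 cm²
- Square 5 × 5 cm, P = 20 cm: 12.70 + 1.27 = 14.0 cm²
- Rectangle 2.5 × 10 cm, P = 25 cm: 15.88 + 1.27 = 17.1 cm²

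Relative to the field, this is 12.5/25 = 50%, 14.0/25 = 56% and 17.1/25 = 69%. As a share of all skin that receives ointment, it is 12.5/37.5 = 33%, 14.0/39.0 = 36% and 17.1/42.1 = 41%.

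With d = 2 cm (π × 2² = 12.57 cm²), the whole band below the extent criterion is 48.0, 52.6 and 62.6 cm² for the same shapes. The 2 cm criterion is 2/0.635 = 3.1 times the width of the treated margin. With the border at the 2.5 cm limit of section 11.2, a reaction could come within 2.5 − 2 = 0.5 cm of the lip or palpebral fissure without meeting the extent criterion.

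**The case against.** A reader might infer that these reactions are recorded nowhere. The documents do not support that. Section 10.3.3 requires abnormal skin findings to be recorded at physical examination, which is a listed safety endpoint (section 8) and is to be compared with baseline (section 17.4). The prescription and dose-adjustment routes in 15.1.2 apply at any extent, so a reaction that changes management reaches the AE tables. Near the eye or mouth, the examination also covers the external eyes and oral cavity. What escapes is milder reaction and spread.

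The examination does not close the gap. It requires no grade and no distance, its findings do not enter the LSR score, and it is not scheduled at Week 13. Because a skin lesion is clinically significant only if it needs treatment at the time, an untreated margin reaction does not become an AE through the examination clause of 15.1.1.

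It is also fair to object that the areas measure skin, not missed reactions. Ointment goes on at the centre and is spread outward, and nothing in the documents suggests that the margin gets more drug or reacts more than the field. That stands, so the percentages should not be read as an under-reporting rate.

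Finally, the margin-only case turns on an undefined term, so it is an ambiguity and not a proven hole. That also stands, but only for that case. The loss of extent, and of a worse grade outside the border, does not depend on it.

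**Conclusion.** The point holds in a limited form. For a reaction that needs no prescribed medication or dose adjustment, spread of up to 2 cm and any worse grade on the treated margin are captured by neither the LSR score nor, under 15.1.2, the AE tables. The margin is 12.5 to 17.1 cm² under the three assumed shapes, or 50% to 69% of the scored area. The remaining record is an ungraded examination finding at four post-baseline visits out of the five at which LSR is scored.

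The effect on reported tolerability cannot be sized, because the documents do not say how often reactions are confined to the margin or worse there. If the field always reacts at least as strongly, the score is right and only extent is lost. Otherwise the score is too low. Separately, sites may differ in whether they report a margin-only reaction as an AE, which would make local AE rates inconsistent between sites.

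**What to change.** Leave the in-field LSR score and its anchors as they are. On the LSR form, and in sections 22.1 and 10.3.7, add two items at the Day 1 baseline and at each later LSR visit, including Week 13:

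1. the greatest distance in cm that any reaction extends past the border;
2. a separate worst 0-4 grade for the surrounding skin out to 2 cm, including the 1/4-inch treated margin.

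Summarize both beside the LSR score by cohort and visit. Reconcile 15.1.2 with 22.1 so that a reaction confined to the margin has one stated place of recording.

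Enlarging the scored area to the field plus 2 cm is a tempting shortcut but would do harm. Several anchors are defined by the share of the Treatment Field involved. For a 5 × 5 cm field the enlarged square is 9 × 9 = 81 cm², so redness over the entire original field would cover only 25/81 = 31% of it and could drop to grade 0. A separate margin grade avoids this and keeps the in-field score comparable with earlier studies.

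The cost is two form fields per visit at visits already scheduled, plus wording in three sections. The margin grade will have no counterpart in earlier studies. No dosing or treatment rule changes.
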